4 STUDY EVENTS FLOW CHART

Intervention and outcomes	Screening Visit	Baseline	4 weeks	8 weeks	6 months	12 months
Eligibility and informed consent	x					
Urine Pregnancy Test (if indicated)	x					
UDI-6	x					
Medical History	x	*				
MESA questionnaire	x					
POP-Q	x [#]			x		
Brinks Scale		x [*]		x		
Primary Outcome Measures (PFDI, PGI-I, PGI-S)		x	x	x	x	X
PFDI, WHODAS, PISQ-IR, McGill Pain Questionnaire, SESPPFE, PGI-S, PGI-I, PFIQ		x	x	x	x	X
PFM performance assessment (PFDx)		x	x	x		
3-day voiding diary	x (before baseline visit)			x		
CGI-S, CGI-I	x			x		
Complications			x	x		
Follow up questions detailing further treatments for SUI					x	X

*May be done at screening visit if < 3 months prior to baseline visit

May be from a visit within 3 months of baseline visit.

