7.2 Study Endpoint(s)

Efficacy:

Efficacy, the primary outcome will be evaluated following 8- weeks of treatment at an in-person interview by study personnel blinded to randomization, and then again by phone and email or mail at 6- and 12- months. Two validated measures will be used to evaluate primary outcomes. First, the patient global impression of improvement (PGI-I), with success was defined as a response of “much better” or “very much better”. Second, the Pelvic Floor Distress Inventory (PFDI-20) urinary distress inventory (UDI-6), with success defined as the absence of bothersome stress incontinence symptoms as indicated by an answer of “no” to the stress incontinence subscale items OR a response of “yes” but with a bother of “not at all” or “somewhat. Other responses will not be considered successes.

Safety and Tolerability:

1. Reported Adverse Events (AEs) and Serious Adverse Events (SAEs)

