8 INVESTIGATIONAL PLAN

8.1 Overall Study Design and Plan

- A prospective, nested, randomized multicenter controlled study to evaluate the efficacy of using the leva® Plus Digital Pelvic System to perform PFME in comparison to Kegel exercises.
- Subjects will be patients referred to a Urogynecologist's office for evaluation.
- Following completion of baseline screening and consent, patients will be randomized by study coordinators at the baseline office visit using an automated randomization system.
- Patient population: women with moderate to severe SUI or stress-dominant mixed urinary incontinence.
- The duration of participation is 8- weeks, with expected post-intervention follow up surveys 6- and 12-months after study terminus.
- Up to 75 participants per site will be enrolled for a total of 225 subjects in the trial.

STUDY ENROLLMENT

The women interested in the study will be screened for participation based on inclusion/exclusion criteria and the MESA questionnaire identifying stress or stress-dominant mixed incontinence, and the UDI-6 (score > 25).

Screening visit: The study will be explained by the study staff and the consent will be reviewed with prospective participants.

- 1) The following questionnaires will be administered:
 - a. MESA
 - b. UDI-6
- 2) Pelvic exam will be performed including:
 - a. POP-Q (acceptable to report from an exam within 3 months of baseline)
 - b. Pelvic floor muscle assessment (Brink Scale) (may be performed at baseline or screening visit (if screening < 3 months prior to baseline)
- 3) If the eligibility requirements are met, patients should be given a 3-day voiding diary (acceptable if reported within 3 months of baseline visit)

The consent will be obtained by the licensed physician investigators or study assistants. Study participation will be entirely voluntary.

STUDY PROCEDURES

Once patients have undergone the appropriate screening evaluation, met criteria for study participation, and provided informed consent, subjects will be randomized to one of two study arms. The "Kegel" arm will involve patient education and performance of Kegel exercises, the current standard of care. The "Leva" arm of the study will undergo patient education and performance of pelvic floor muscle exercises using the Leva system. Subjects in the "Leva" arm will be sub-randomized to one of two long term follow up plans, follow up without reminders or follow up using automated reminders by text message.

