10.1.1 Determination of Sample Size

This planned randomized controlled trial is a tertiary prevention trial, comparing the efficacy of the Leva device in the treatment of stress urinary incontinence to standard pelvic floor muscle training, consisting of office education and a home exercise program. Our primary outcome is the proportion of subjects who are very much better/much better as measured by the PGI-I. Sample size for 20% difference between groups given a 30% success rate of home exercise programs, $\alpha=0.05$, and a power of 0.8, the needed sample size is 93 patients in each arm. Allowing for an attrition rate of approximately 15%, we require approximately 225 patients.

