3.3 Compliance

Compliance will be assessed by participant report at the 8-week study visit. Participants who report performing the exercises at least 80% of the time will be considered compliant. Exercises using the leva[®] Plus Pelvic Digital Health System should be performed twice daily, for a total of 14 times per week; therefore, participants who perform the exercise at least 11 times per week will be considered compliant. Exercises in the control (Kegel) arm should be performed three times per day, for a total of 21 times per week; therefore, participants who perform the exercises 17 times per week will be considered compliant.

In addition, for participants in the leva[®] Plus Pelvic Digital Health System arm, self-report will be validated using data from the device. The distribution of concordance will be reported. Allowing for some error in reporting, reports within 1 exercise per week (over or under report) will be considered concordant. This may be altered based on the data, at which point the statistician and investigators may re-define concordance.

3.4 8-week assessment

The primary outcome, 8-week assessment, will be reported as described below. Efficacy will also be reported as both improvement on the PGI-I and no urinary distress on the PFDI-20. In addition, the results of the PFDI, PISQ-IR, McGill Pain Questionnaire, SESPPFE, WHODAS, PFIQ, PGI-S and clinical assessment of urinary incontinence (voiding diary, POP-Q, PFDx device assessment) will be reported.

Efficacy of leva[®] Plus Pelvic Digital Health System: Two definitions of efficacy will be reported as two “primary” outcomes. Both will be dichotomous (yes or no). Efficacy will be assessed at the 8-week visit and will be defined as: 1, improvement of symptoms, and 2, no urinary distress.

- “Improvement” will be defined as “much better” or “very much better” on the Patient Global Impression of Improvement (PGI-I) scale. Any other answers will be considered “No improvement”.
- “No urinary distress” will be defined as a raw score of 2 or less on all six indicators in the Pelvic Floor Disability Index (PFDI-20) Urinary Distress Inventory (UDI-6) subscale. Raw scores of greater than 2 will be considered reports of distress.

Both will be reported as the primary study outcome.

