- **Pelvic Floor Disability Index (PFDI):** Obtain the mean value of all of the answered items within the corresponding scale (possible value 0 to 4) and then multiply by 25 to obtain the scale score (range 0 to 100). Missing items are dealt with by using the mean from answered items only. For the summary score, add the scores from the 3 scales together to obtain the summary score

(range 0 to 300). This can be reported as a continuous variable or may be categorized depending on distribution of the data. For the primary outcome, “No urinary distress” will be defined as a raw score of 2 or less on all six indicators in the UDI-6 subscale. Raw scores of greater than 2 will be considered reports of distress.

- **Pelvic Organ Prolapse/Urinary Incontinence Sexual Questionnaire (PISQ-IR):** Validated scoring available from Constantine, M.L., Pauls, R.N., Rogers, R.R. et al. *Int Urogynecol J* (2017) 28: 1901.
- **McGill Pain Questionnaire:** The level of pain for each word can be reported as None, Mild, Moderate, Severe. Collapsing of responses is also possible (pain vs. no pain, no/mild pain vs. moderate/severe pain). Reporting of the visual analogue scale will depend on data recording. Reports of pain location will need to be manually reviewed and categorized.
- **Self-Efficacy Scale for Practicing Pelvic Floor Exercises (SESPPFE):** Sum all of the scores to calculate total score for the scale. This can be reported as a continuous variable or may be categorized depending on distribution of the data.
- **Patient Global Impression of Improvement (PGI-I) Scale:** This is only a single question and will be dichotomized as improvement (“very much better” or “much better”) vs. no improvement (all other non-missing answers).
- **Patient Global Impression of Severity (PGI-S) Scale:** This is only a single question and can be reported as is.
- **World Health Organization Disability Assessment Schedule (WHODAS):** Two options are available for scoring the WHODAS. The first is a simple summary score as a continuous variable. The second option is to use the available coding provided by the WHO (http://apps.who.int/iris/bitstream/handle/10665/43974/9789241547598_eng.pdf;jsessionid=680B7F5F1FC5DE085FA4DCFD302F1176?sequence=1). A score of 17 or greater constitutes significant disability.

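### SAP 3.4 counts UDI-6 success on all six items where Protocol 7.2 uses only the stress items, without disclosing the change; the number of primary outcomes and the success rule are also unreconciled

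*SAP*

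**What the plan says.** **UDI-6 success.** Protocol 7.2 has "success defined as the absence of bothersome stress incontinence symptoms". A woman qualifies if she answers no to the stress items, or yes with a bother of *not at all* or *somewhat*. SAP 3.4 instead asks for a "raw score of 2 or less on all six indicators in the Pelvic Floor Disability Index (PFDI-20) Urinary Distress Inventory (UDI-6) subscale", and its PFDI scoring paragraph repeats the rule.

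**Number of primaries.** Protocol 10.1.1: "Our primary outcome is the proportion of subjects who are very much better/much better as measured by the PGI-I". It gives no time point. Protocol 7.2: "Two validated measures will be used to evaluate primary outcomes", evaluated after 8 weeks. SAP 3.4 also has two: "Both will be reported as the primary study outcome". The Protocol Section 4 flow chart has a row labelled "Primary Outcome Measures (PFDI, PGI-I, PGI-S", which adds PGI-S.

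**Use of the results.** SAP 3.5 plans log-binomial risk ratios to judge whether the device worked, for improvement, for distress and for the two combined, with a general two-sided 0.05 threshold. SAP 3.2.2 also compares the primary outcomes between women who did and did not call about technical problems.

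**Status.** SAP 2 says that the trial ended early, enrolled 60 women (30 per arm) and will be analysed as a pilot. The SAP 1 objectives are feasibility, technical issues and compliance. SAP 3.5 says the data will be examined descriptively and asks for caution in reporting the primary analysis.

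**The concern.** The two documents sort the same questionnaire answers into different responder groups. The women affected are those whose stress items are quiet but who are bothered by another urinary item. They are plausible here, because Protocol 8.1 admits "women with moderate to severe SUI or stress-dominant mixed urinary incontinence". The change reaches the UDI-6 outcome, the combined outcome and the SAP 3.2.2 comparison. Because the SAP was written after the study stopped and is silent on the point, a reader who holds both documents cannot tell whether the change was deliberate.

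The second issue is what counts as a positive result. One section sizes the trial on PGI-I, two sections name two primaries, and three efficacy assessments share one threshold. Nothing says whether one result is enough, both are needed, or the combination decides. A single p-value below 0.05 from 60 women could then be read as showing efficacy.

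**Working it through.** **1. The plan's own sample size.** Inputs from Protocol 10.1.1: 30% v 50%, alpha 0.05 (taken as two-sided), power 0.80. Pooled formula, mean rate 0.40:

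n = [1.960 × √(2 × 0.40 × 0.60) + 0.842 × √(0.30 × 0.70 + 0.50 × 0.50)]² / 0.20² = 93.0 per arm.

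This matches the stated 93. Then 186 / 0.85 = 219, and the stated figure of about 225 corresponds to 1 − 186/225 = 17% attrition. The calculation is sound, for PGI-I alone.

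**2. Direction of the UDI-6 difference.** Assumption: *no*, *not at all* and *somewhat* are raw scores 0, 1 and 2. This fits the 0 to 4 item range in SAP 3.4 but is not stated. Protocol success is then all stress items at 2 or less, and SAP success is all six items at 2 or less. The second group lies inside the first, so the SAP rate cannot be the higher one.

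**3. Possible size.** The documents give no rates. Suppose 40% are Protocol successes (12 of 30) and a fraction f of them have another item above 2. The SAP rate is 0.40 × (1 − f):

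| f (assumed) | SAP rate | Of 30 |
|---|---|---|
| 0.10 | 36% | 10.8 |
| 0.25 | 30% | 9 |
| 0.50 | 20% | 6 |

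**4. Effect on the comparison.** Take 15/30 v 9/30 for illustration (the planned PGI-I rates, assumed for UDI-6).

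- Before reclassification: RR = 1.67; SE of log RR = √(1/15 + 1/9 − 2/30) = 0.333; 95% CI 0.87 to 3.20.
- With one third of successes reclassified in each arm, 10/30 v 6/30: RR = 1.67; SE = √(1/10 + 1/6 − 2/30) = 0.447; 95% CI 0.69 to 4.00.

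Equal reclassification widens the interval and leaves the estimate where it was. Only a different fraction in each arm would move it.

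**5. False positives if any one result could count.** Simulation at 30 per arm with no true difference. The PGI-I rate is 30% (Protocol 10.1.1). Assumed: UDI-6 rate 30-50% and latent correlation 0-0.9. The Wald test on the log risk ratio stands in for the planned log-binomial model.

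| | Chi-square | Wald log-RR |
|---|---|---|
| PGI-I alone, both directions | 4.9% | 3.6% |
| Two outcomes, both directions | 8-10% | 6-9% |
| Plus combined, both directions | 9-13% | 7-10% |
| Two outcomes, favouring device | 4-5% | 3-4% |
| Plus combined, favouring device | 5-7% | 3-5% |

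The nominal levels are 5% for both directions and 2.5% for one. With Fisher's exact test the rates in both directions are 4-5% for two outcomes and 5-7% for three. If both primaries had to be significant, the rate when neither differs is at most 1.6% in these settings.

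**The case against.** The strongest reply is that the SAP is coherent on its own terms. It names both outcomes as primary, gives the same all-six rule twice, and governs a pilot whose objectives do not include an efficacy test. This stands in part: the conflict lies between the documents, not inside the SAP, and the pilot status limits its weight. But the SAP refers to the Protocol for the study's design, departs from its endpoint without saying so, and keeps both the threshold and the efficacy wording. A descriptive proportion also needs one definition.

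It can also be said that the stress-item rule is not self-evidently better, since eligibility uses the whole UDI-6 score. That is fair. The case for it is that it is the Protocol's endpoint and fits the stress-incontinence objective.

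Several stronger readings are tempting and not supported:

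- **The definition was changed to suit the results.** The SAP postdates the end of the study, but nothing says who had seen which data or why the rule differs.
- **The all-six rule biases the comparison.** No figure shows unequal reclassification between arms.
- **The error rate is 9-13%.** This needs a rule that any one result counts, which no section states or excludes. It also includes results favouring Kegel exercises, while the hypothesis is superiority of the device.
- **PGI-I is the only legitimate primary.** A sample-size sentence does not clearly override an endpoint section, and demoting UDI-6 after the study ended would be another late change.
- **PGI-S is a third primary.** The flow-chart row is a labelling inconsistency; no success definition goes with it.

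**Conclusion.** The point holds in two parts of unequal weight, and should be corrected.

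The main part is the undisclosed change in who counts as a UDI-6 success. That the item sets differ is plain from the text. That the SAP rate is equal or lower rests on *somewhat* being raw score 2. The size of the drop is unknown; the 36% to 20% range is illustrative. The documents support a possible loss of precision, not a shift in the risk ratio.

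The lesser part is the mismatch between one and two primaries, with three assessments and no success rule. Under the least favourable rule, and the assumed rates and correlations, false results in favour of the device would be roughly 3-7% against 2.5%. This is minor given the pilot status and the SAP's own call for caution. The figure of 93 per arm is unaffected.

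**What to change.** - **SAP 3.4, both places:** use the Protocol 7.2 stress-item definition for UDI-6 success, and report the all-six version as a labelled additional analysis. If the all-six rule was deliberate, state when and why it was adopted and report both versions.
- **Combined outcome and the SAP 3.2.2 comparison:** apply the same definition.
- **Primary label:** disclose that Protocol 10.1.1 sized the trial on PGI-I only, while Protocol 7.2 and SAP 3.4 name two primaries. UDI-6 need not be demoted.
- **SAP 3.5:** give the purpose of the risk ratios as estimating the difference between arms. State that the 0.05 threshold will not be used to claim efficacy from the 60-woman pilot. Report all three risk ratios with 95% confidence intervals.
- **Protocol Section 4:** align the primary-measures row with the endpoint section.

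The PFDI is already collected at week 8, so no new data are needed. The cost is slightly more reporting, and no significance claim on efficacy from the pilot.

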3.5 General statistical analysis guidelines

The analyses will be conducted in the entire population. The denominator for all data will be the total number of women randomized to each group. Two-sided p-values less than 0.05 will be considered statistically significant.

Normality of continuous variables will be assessed using the Shapiro-Wilkes test and a visual inspection of the data distribution. Continuous variables that are normally distributed will be reported as means \pm standard deviation. Non-normally distributed data will be reported as median and interquartile range (25th and 75th percentile). Categorical variables may be collapsed as necessary depending on data distribution, although all efforts will be made to maintain pre-determined categories. Categorical variables will be presented as n (%).

Data will be examined descriptively. Crude proportions of the primary and secondary outcomes at 8 weeks will be reported. Log-binomial regression will be used to calculate risk ratios and 95% confidence intervals (CIs) to assess whether the intervention was efficacious. We will assess each portion of efficacy separately (improvement and distress) as well as combined. If differences between the intervention and control groups as seen as baseline, these may be adjusted for in a log-binomial regression.

Chi-square or Fisher's exact tests may be used to calculate p-values to assess differences between categorical variables, as appropriate based on distribution of the data. To assess differences in normally distributed continuous variables between groups, the Student's T-test will be used to calculate p-values. To assess differences in non-normally distributed continuous variables between groups, the Wilcoxon rank-sum test will be used. Log-binomial regression will be used to calculate risk ratios and 95% CIs to assess the association between the intervention and all categorical variables. Linear regression will be used to calculate difference in means and 95% CI to assess the relationship between the intervention and all continuous variables.

In the event that the log-binomial regression does not converge, modified Poisson regression with robust standard errors will be substituted. If this is consistent problem, the statistician may decide to use this approach for all calculations of risk ratios and 95% CIs.

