Due to the nature of the pilot/feasibility study, results of the primary analysis should be reported with caution. The initial sample size and follow up time was not achieved.

4. Additional comments

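### Some women can already meet the primary outcome *no urinary distress* at entry; the SAP does not count them by arm and leaves baseline adjustment optional

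*SAP*

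**What the plan says.** **Outcome.** SAP 3.4 sets two dichotomous efficacy outcomes at 8 weeks, PGI-I improvement and *no urinary distress*, and adds "Both will be reported as the primary study outcome". The second "will be defined as a raw score of 2 or less on all six indicators in the UDI-6 subscale". It requires neither distress at baseline nor a change from baseline. SAP 3.4 and 3.5 also plan to report the two outcomes combined.

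**Scoring.** SAP 3.4 takes the mean of the answered items (0 to 4), then says to "multiply by 25 to obtain the scale score (range 0 to 100").

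**Entry.** Protocol 8.3.1 requires a UDI-6 score of at least 25; the enrolment text in Protocol 8.1 says above 25. The other symptom-score rule, on the MESA, is relative (stress above urge). The moderate-to-severe description in Protocol 8.1 has no item-level rule attached.

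**Analysis.** SAP 3.5 says "Crude proportions of the primary and secondary outcomes at 8 weeks will be reported" and "The denominator for all data will be the total number of women randomized to each group". If baseline differences are seen, "these may be adjusted for in a log-binomial regression"; no covariate is named. SAP 3.1 has baseline PFDI results reported for both groups, and SAP 3.4 allows the scale to be continuous or categorised.

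**The concern.** The entry rule is a floor on the item average, while the outcome is a ceiling on each item. The floor is low enough that both can hold at once. A woman in that position counts as an 8-week success simply by staying as she was. Such women add the same expected amount to both arms and so pull the risk ratio toward 1. At 30 women per arm they can also fall unevenly by chance.

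The planned baseline PFDI report would not show how many there are. A scale score between 25 and 50 does not reveal whether every item is 2 or less. Without the count by arm, a reader cannot tell whether a weak result reflects little effect or little room to respond, or whether an apparent effect reflects an uneven start. A pilot should be able to answer whether this endpoint leaves room for response.

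**Working it through.** **Inputs from the documents.** Item range 0 to 4 and multiplier 25 (SAP 3.4); entry threshold 25 (Protocol 8.3.1; above 25 in 8.1); 30 women per arm (SAP 2); two-sided 0.05 (SAP 3.5); success rates of 30% and 50% (Protocol 10.1.1). Those rates were set for the PGI-I and are borrowed here only as an illustration.

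**Plan's own figure.** (1.960·√(2·0.4·0.6) + 0.842·√(0.3·0.7 + 0.5·0.5))² / 0.2² = 93.0, which reproduces the protocol's 93 per arm. That sample size rests on the PGI-I, so this point does not touch it.

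**Step 1: overlap.** Score = (item total / 6) × 25, with all six items answered.
- Entry at 25 or more: total at least 6.
- Entry above 25: total at least 7, score 29.2.
- Outcome met: every item at most 2, so total at most 12, score at most 50.

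A woman answering 1 on every item scores 25 and meets both rules. One answering 2 on every item scores 50 and meets both under either threshold. Of the 3⁶ = 729 answer patterns that meet the outcome, 435 also meet entry at 25 or more, and 294 at above 25. These are counts of patterns, not of patients.

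**Step 2: dilution.** Let s be the share of women in each arm who already meet the outcome, and assume they all stay successes. The success rates are s + (1 − s)·0.30 and s + (1 − s)·0.50. Power uses the two-proportion formula with pooled variance.

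| s | Control | leva | Risk ratio | Power, 30 per arm |
|---|---|---|---|---|
| 0% | 30.0% | 50.0% | 1.67 | 35% |
| 5% | 33.5% | 52.5% | 1.57 | 31% |
| 10% | 37.0% | 55.0% | 1.49 | 28% |
| 20% | 44.0% | 60.0% | 1.36 | 23% |
| 30% | 51.0% | 65.0% | 1.27 | 19% |

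If only 90% of these women stay successes, the risk ratios at 5 to 30% are 1.58, 1.50, 1.38 and 1.29.

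**Step 3: chance imbalance.** With two independent Binomial(30, s) counts, the probability that the arms differ by 4 or more such women is 4, 13, 26 and 32% at s = 5, 10, 20 and 30%. For example, take 8 versus 4 women with 30% success among the rest in both arms. The expected rates are (8 + 0.3·22)/30 = 48.7% and (4 + 0.3·26)/30 = 39.3%, a crude risk ratio of 1.24 with no treatment effect. That split needs 12 of 60 women (20%) to qualify.

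**Step 4: what adjustment does.** Modified Poisson regression on arm and baseline status has a large-sample risk ratio of 1.57, 1.49, 1.36 and 1.27 at s = 5, 10, 20 and 30%, the same as unadjusted. It does not remove dilution. It affects precision, as 10,000 simulated trials per share show:

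| s | Power adjusted | Power unadjusted |
|---|---|---|
| 2% | 31.5% | 33.0% |
| 5% | 30.6% | 31.1% |
| 10% | 29.4% | 28.6% |
| 20% | 28.3% | 23.6% |
| 30% | 26.4% | 20.0% |

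Type I error with adjustment was 3.9 to 5.5%.

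**Step 5: restricted analysis.** Leaving out women who meet the outcome at baseline keeps about 30·(1 − s) per arm: 28, 27, 24 and 21 at s = 5, 10, 20 and 30%. Under the illustration its risk ratio is 1.67 by construction.

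**The case against.** The case against is mainly about weight, and much of it stands.

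- **The share is unknown.** Nothing in the documents gives baseline item answers. A reader might take 435 of 729 patterns as a sign that many women qualify; pattern counts say nothing about frequency. At 5% or below the effect is small.
- **No bias in expectation.** A reader might infer that the comparison is biased. It is not: the outcome is a state at 8 weeks, randomisation balances baseline status on average, and the unadjusted confidence interval covers chance imbalance on average.
- **Other outcomes are protected.** PGI-I is largely unaffected. The combined outcome also requires PGI-I improvement, so these women cannot pass it automatically.
- **Partly handled.** Baseline PFDI is reported and may be categorised, and differences may be adjusted for. What is missing is small.
- **Adjustment is no cure.** A reader might expect it to undo the dilution. Step 4 shows that it does not, and it gains clearly only at shares of about 20 to 30%.
- **The model is not at fault.** The unadjusted log-binomial model is suitable, and SAP 3.5 already provides a fallback: "In the event that the log-binomial regression does not converge, modified Poisson regression with robust standard errors will be substituted".
- **This is a pilot.** Its objectives are feasibility, technical issues and compliance, and the SAP says "results of the primary analysis should be reported with caution".

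What remains is that SAP 3.5 still plans risk ratios and a 0.05 threshold to judge efficacy on this outcome, without the one count needed to read it.

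**Conclusion.** The point holds and is minor. Entry and outcome overlap for UDI-6 scores of 25 to 50 (29.2 to 50 if the threshold is above 25), and no other criterion requires an item above 2. The SAP requests no count of such women by arm, and adjustment is left to a choice made after seeing the data. The consequence is dilution and loss of precision on one of two primary outcomes, from slight at a 5% share (1.67 to 1.57) to substantial at 30% (1.27).

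Assumptions: the screening UDI-6 is scored as in SAP 3.4 with all items answered; women who meet the outcome at entry mostly stay successes; the borrowed 30% and 50% apply to the rest. The screening UDI-6 and the baseline PFDI may come from different visits unless these are combined (Protocol 4 and 8.1.1), so status can change between them.

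A reader might think that the protocol's stress-item definition (Protocol 7.2) avoids the problem. It restricts only some of the six items, so any woman who meets the SAP definition also meets it, assuming that its two accepted bother answers correspond to raw scores of 2 or less.

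**What to change.** 1. **SAP 3.1:** report, by arm, the number of women meeting *no urinary distress* at baseline.
2. **SAP 3.4:** add a supportive analysis restricted to women who do not meet it at baseline, using the items of the definition finally adopted. This is the step that addresses dilution.
3. **SAP 3.5:** for this outcome, replace the optional, difference-triggered adjustment with a prespecified adjustment for baseline status by the modified Poisson model already named there. Show it beside the unadjusted risk ratio, with all randomised women as the denominator. If no woman meets the outcome at baseline, the unadjusted model stands.

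Two separate discrepancies should be reconciled in their own right: the UDI-6 threshold (Protocol 8.1 against 8.3.1), and the stress items of Protocol 7.2 against all six items in SAP 3.4.

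**Cost.** A few sentences and one table row. Baseline PFDI is already collected before randomisation (Protocol 8.1, Visit 1). The restricted analysis has fewer women and less precision. At shares of 2 to 5%, adjustment gains no power (about 0.5 to 1.5 points lower in simulation).
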